
 • To evaluate the efficacy of idasanutlin monotherapy: 
 – by Hct control without phlebotomy 	
 • Hct control is defined as protocol-specified ineligibility for phlebotomy between Week 8-Week 32 and ≤1 instance of phlebotomy eligibility between first dose and Week 8 
Definition of eligibility for phlebotomy: a Hct of ≥45% that was ≥ 3% higher than baseline level or a Hct of >48%

Secondary	

 • To evaluate the efficacy of idasanutlin monotherapy by complete hematologic response • To evaluate the efficacy of idasanutlin monotherapy by using modified ELN hematologic response criteria (complete and partial response) in patients with baseline splenomegaly, patients without baseline splenomegaly and in all patients irrespective of spleen size 	
 • Complete hematologic response at Week 32 
Complete hematologic response requires all of the following:
 
 – Hct control (protocol-specified ineligibility for phlebotomy between Weeks 8–32 and ≤1 instance of phlebotomy eligibility between first dose and Week 8); – White blood cell count ≤10 ×10⁹/L at Week 32 assessment; AND – Platelet count ≤400 ×10⁹/L at Week 32 assessment 
 • Complete hematologic remission at response Cycle 11 Day 28 defined as patients with all of the following: 
 – Hct control defined as protocol specified ineligibility for phlebotomy between Week 32 assessment and Cycle 11 Day 28 – White blood cell count ≤10 ×10⁹/L at Cycle 11 Day 28 assessment; AND – Platelet count ≤400 ×10⁹/L at Week 32 assessment • Duration of complete hematologic remission response with a durable responder defined as a subject in complete hematologic remission at Week 32 and Cycle 11 Day 28, as defined above • Response by using modified ELN hematologic response criteria: 
 – Complete response – Partial response – NR – Progressive disease, as defined by increased bone marrow fibrosis from baseline, and/or transformation to MF, MDS or acute leukemia • Duration of response, including proportion of patients with durable response lasting at least 12 weeks from Week 32 (Hct control, CHR, ELN 2009 response and composite response, if applicable)

Objectives	Endpoints

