3. OBJECTIVES AND ENDPOINTS

The objectives and corresponding endpoints are provided in [Table 3](#).

Table 3 Objectives and Endpoints

Ruxolitinib Naive Patients:

Objectives	Endpoints
Primary	

 • To evaluate the efficacy of idasanutlin monotherapy in patients with HU resistant/intolerant PV and without prior ruxolitinib exposure: 
 – For patients with splenomegaly at baseline using composite response criteria – For patients without splenomegaly at baseline by Hct control without phlebotomy – For all patients (with and without splenomegaly) by Hct control without phlebotomy 	
 • Composite response at Week 32 for patients with splenomegaly at baseline (per inclusion criteria) defined as: 
 – Hct control defined as protocol-specified ineligibility for phlebotomy between Week 8-Week 32 and ≤ 1 instance of phlebotomy eligibility between first dose and Week 8 – $\geq 35\%$ reduction in spleen volume at Week 32 • Hct control in patients without splenomegaly at baseline and in all patients (with and without splenomegaly); defined as protocol-specified ineligibility for phlebotomy between Week 8–Week 32 and ≤ 1 instance of phlebotomy eligibility between first dose and Week 8 
Definition of eligibility for phlebotomy: a Hct of $\geq 45\%$ that was $\geq 3\%$ higher than baseline level or a Hct of $> 48\%$

Secondary	

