4.1.2 Dose-Escalation Decision Criteria

Intra-patient dose-escalation from 150 mg to 200 mg may be allowed *at Cycle 4 or 5* for patients who have demonstrated adequate tolerability *but have a lack of Hct control or inadequately controlled leukocytosis and/or thrombocytosis at the end of Cycle 3*. The goal is to bring these patients to a *better* hematologic response by end of Cycle 5 to allow for assessment for durability of response through Week 32. PK samples will be taken from these dose-escalated patients at the beginning of Cycle 4 to assess PK characteristics at the higher dose compared to Cycle 1.

Patients with progressive disease will not be permitted to dose-escalate and the patient should come off the study.

Consideration for dose-escalation will be based on a review of patient data, including but not limited to, response assessments, laboratory, and safety data. All intra-patient dose-escalation decisions will be made in consultation with the Investigator and Sponsor, including the Medical Monitor and Safety Science Leader.

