6.6 DOSAGE MODIFICATION

Intra-patient dose-escalation from 150 mg to 200 mg is allowed after Cycle 3 (*preferable at Cycle 4, or latest, Cycle 5*) for patients who have demonstrated adequate tolerability and are showing a lack of Hct control *and/or inadequately controlled leukocytosis and/or thrombocytosis* at end of Cycle 3 (Section 4.1.2). Patients with PD will not be permitted to dose-escalate and should come off the study. Consideration for dose-increase will be based on a review of patient data, including but not limited to, safety data, response assessments and laboratory data. All intra-patient dose-escalation decisions will be

made in consultation with the Investigator and Sponsor, including the Medical Monitor and Safety Science Leader.

In case of hematologic toxicity (i.e., anemia, thrombocytopenia and/or neutropenia), patients may need treatment interruptions and/or dose reductions (see Table 8).

Guidance for dose-reductions for AEs is described in Section 8.3.9. Furthermore, after one year of treatment (end of Cycle 13), a reduction of the idasanutlin dose to 100 mg for all subsequent cycles may occur for any patient that has not previously had a reduction to 100 mg for other reasons to generate data for longer term tolerability. This reduction will be based on communication between the Investigator and Sponsor. Treatment may be re-escalated back to the prior highest tolerated dose if Hct increases to $\geq 45\%$ and/or CHR response is lost ($WBC \geq 10 \times 10^9/L$ and PLT count $> 450 \times 10^9/L$) to achieve a hematologic response. Treatment *must* not be re-escalated if the patient has progressive disease (see Appendix 1).

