A treatment break may also be exercised if sufficient clinical response (CHR/Hct control) is ongoing at end of Cycle 13 or in subsequent cycles. For these patients, unscheduled hematologic response assessments should occur every 28 days and unscheduled full response assessment (as defined on SoA as for Week 32) should occur every 84 days, if treatment holiday is prolonged. Treatment may resume if Hct increases to $\geq 45\%$ and/or CHR response is lost ($WBC \geq 10 \times 10^9/L$ and PLT count $> 450 \times 10^9/L$). Treatment will thereafter continue until 2 years post initial dose. Treatment should not be re-initiated if the patient has progressive disease. If subsequent scheduled efficacy assessment after re-escalation indicate a lack of Hct control ($\geq 45\%$) or NR by ELN 2009, treatment should be discontinued.

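### Section 6.6 ties lack of Hct control to a flat Hct ≥45%, the endpoint defines control by phlebotomy ineligibility, and the Cycle 3 escalation rule gives no threshold

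*Protocol*

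**What the plan says.** **Endpoint.** Protocol Section 3 (Table 3) gives "Hct control defined as protocol-specified ineligibility for phlebotomy between Week 8-Week 32", with at most one eligible instance between first dose and Week 8. The Synopsis uses the same definition for ruxolitinib-resistant or intolerant patients, and SAP Section 5.7.1 repeats it. Eligibility needs Hct ≥45% that is also ≥3% above baseline, or Hct >48%. The Appendix 1 footnote applies the same definition to the Hct criterion of ELN complete and partial response.

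**Stop rule.** The closing sentence of Section 6.6 begins "If subsequent scheduled efficacy assessment after re-escalation indicate a lack of Hct control". With its threshold and action, it reads "indicate a lack of Hct control ($\geq 45\%$) or NR by ELN 2009, treatment should be discontinued". It has no baseline condition. Section 6.6 also uses Hct ≥45% as the level for re-escalating and for resuming after a break.

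**When the stop rule applies.** The reduction that re-escalation follows comes "after one year of treatment (end of Cycle 13), a reduction of the idasanutlin dose to 100 mg". The alternative is a pause: "A treatment break may also be exercised if sufficient clinical response (CHR/Hct control) is ongoing at end of Cycle 13".

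**Escalation to 200 mg.** Section 4.1.2 allows it for patients who "have a lack of Hct control or inadequately controlled leukocytosis and/or thrombocytosis at the end of Cycle 3". The Synopsis and Sections 4.1, 4.3 and 6.6 use the same idea. None gives an Hct value or points to a definition.

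**The concern.** One term carries two meanings. Every phlebotomy-eligible Hct is also ≥45%, but the converse is false. At a single assessment, therefore, the conflict runs one way: a patient in control by the endpoint definition can be labelled as lacking control by Section 6.6 and, if the rule is followed as written, taken off drug for want of a response that the protocol's own definition says is present.

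The term also gates escalation at Cycle 4 or 5, before the Week 32 assessment. With no threshold stated there, sites and the sponsor can apply different criteria. The escalated group is then not a defined population, and the mix of 150 mg and 200 mg patients behind the Week 32 rate depends on an unstated choice. That matters most for the ruxolitinib-resistant or intolerant cohort, whose expansion is meant for registration.

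**Working it through.** **Inputs.** Phlebotomy eligibility (Table 3): (Hct ≥45% and Hct ≥ baseline + 3%) or Hct >48%. Section 6.6: lack of control if Hct ≥45%. Entry (Section 5.1): Hct >40%. The documents do not say whether 3% means percentage points or a relative rise, so both are shown.

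**Plan's own figure.** The nearest design figure is the 75% probability of at least 7 of 20 responders at a true Hct control rate of 40% (Section 9.2.2). The binomial tail P(X ≥ 7 | 20, 0.40) = 0.750 reproduces it. It is not in dispute and does not change.

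**Where the two rules disagree.** They disagree when Hct ≥45%, Hct is below the baseline-linked threshold, and Hct ≤48%.

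- Points: this needs baseline + 3 > 45, so baseline > 42%. The band reaches 48% when baseline + 3 > 48, so baseline > 45%.
- Relative: this needs 1.03 × baseline > 45, so baseline > 45/1.03 = 43.69%. The band reaches 48% when baseline > 48/1.03 = 46.60%.

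Band of Hct that is control under Table 3 and lack of control under Section 6.6, in steps of 0.1:

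| Baseline | 3% as points | 3% as relative |
|---|---|---|
| 42% or below | none | none |
| 43% | 45.0–45.9 | none |
| 44% | 45.0–46.9 | 45.0–45.3 |
| 45% | 45.0–47.9 | 45.0–46.3 |
| 46% | 45.0–48.0 | 45.0–47.3 |
| 47% | 45.0–48.0 | 45.0–48.0 |

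**Example that holds under both readings.** Take baseline 46% and a stable Hct of 47%. The baseline-linked threshold is 46 + 3 = 49% (points) or 46 × 1.03 = 47.4% (relative), and 47% is not above 48%. The patient is never eligible, so is in Hct control and, absent progressive disease, at least an ELN partial responder. In Section 6.6 this patient could enter a break as a responder while already at the level for resuming, and after re-escalation would meet the Hct limb of the stop sentence but not its ELN limb.

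**Timing at 28 days per cycle, without delays.** End of Cycle 3 = Week 12. End of Cycle 8 = Week 32. Cycle 11 Day 28 = Week 44. End of Cycle 13 = Week 52. The stop rule therefore acts after both the primary and the 12-week durability assessments.

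**The Week 12 trigger.** The Week 8–32 definition cannot be complete at Week 12, so the term needs an interpretation, and the candidates differ:

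- Phlebotomy-eligible at the Week 12 visit: the patient has already failed Week 8–32 ineligibility, so escalation on this ground cannot yield a primary Hct-control responder.
- Hct ≥45%: patients still in control by the endpoint can be escalated.
- Endpoint definition already failed (two eligible instances before Week 8, or one in Weeks 8–12): this can include a patient with Hct <45% at the end of Cycle 3.

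**The case against.** The strongest reply is that Section 6.6 states its threshold in the sentence itself, and that re-escalating, resuming and stopping all use ≥45%. A site would know what to do after Week 52, so only the label clashes. Table 3 and the Appendix 1 footnote also describe Weeks 8–32, so calling a patient in control after Week 52 extends that definition. This stands in part: the numbers within Section 6.6 agree with each other. But Table 3 itself carries phlebotomy ineligibility beyond Week 32, to Cycle 11 Day 28, and the ELN limb of the stop sentence relies on Appendix 1, so two limbs of one sentence can disagree about the same patient.

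On escalation, the reply is that it is permissive, reviewed case by case with the sponsor, and open separately for leukocytosis or thrombocytosis. That softens the effect but does not define the trigger.

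A reader might infer more than the documents support:

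- *That patients in Hct control must be stopped.* The text says should, and only after re-escalation following a reduction or break at or after the end of Cycle 13.
- *That the 12-week durability endpoint is harmed.* It is read at Cycle 11 Day 28, before the rule can act, and the duration shell in SAP Section 5.7.2.3 reports only response of at least 12 weeks.
- *That the ≥45% value is written into the escalation rule.* It is not. The defect there is a missing threshold.
- *That Section 7.1 conflicts too.* It speaks of an Hct response, gives no threshold and is permissive, so no contradiction is shown.

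**Conclusion.** The inconsistency is real and worth correcting, within limits. The stop wording in Section 6.6 and the endpoint definition disagree for baselines above 42% (points) or about 43.7% (relative), over an Hct band from 45% to at most 48%. The full band to 48% needs a baseline above 45% or above 46.6% respectively, and at baseline 42% or below there is no gap under either reading. The consequence is confined to who stays on drug and is followed for response after about Week 52. The Week 32 and Cycle 11 Day 28 endpoints and the sample-size figures are unaffected by the stop rule.

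The escalation trigger is a separate defect, an undefined term applied at Week 12. It can bear on the primary endpoint because it acts before Week 32.

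A reader might want a percentage of patients affected. The documents give no baseline or on-treatment Hct distribution and no rate of reduction, break or re-escalation, so none can be computed. The conclusion rests on the wording alone and does not depend on how 3% is read. It makes no judgement about which Hct threshold is clinically right.

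**What to change.** Reconcile the Synopsis (treatment groups), Sections 4.1, 4.1.2, 4.3 and 6.6, and Appendix 1 with Table 3. The sponsor should:

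1. state which Hct criterion applies to escalation, re-escalation, resumption and stopping;
2. say how the escalation criterion is judged at the end of Cycle 3, when the Week 8–32 window is still open;
3. keep the term Hct control for one definition, and name any other Hct threshold as such;
4. record on the eCRF which criterion triggered each escalation or stop;
5. report the number of patients escalated or stopped while phlebotomy-ineligible.

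Which threshold belongs in each place is for the sponsor to decide. The cost is protocol wording, one eCRF field and one descriptive count, with no added patients or visits.

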6.7 TREATMENT AFTER THE END OF THE STUDY

The Sponsor will offer post-trial access to idasanutlin free of charge to eligible patients in accordance with the Roche Global Policy on Continued Access to Investigational Medicinal Product.

A patient will be eligible to receive study treatment after the end of the study if all of the following conditions are met:

- The patient has a life-threatening or severe medical condition and requires continued study treatment for his/her well-being.
- There are no appropriate alternative treatments available to the patient.
- The patient and his/her doctor comply with and satisfy any legal or regulatory requirements that apply to them.

A patient will not be eligible to receive study treatment after the end of the study if any of the following conditions are met:

- The study treatment is commercially marketed in the patient's country and is reasonably accessible to the patient (e.g., is covered by the patient's insurance or wouldn't otherwise create a financial hardship for the patient).
- The Sponsor has discontinued development of the study treatment or data suggest that the study treatment is not effective for PV.
- The Sponsor has reasonable safety concerns regarding the study treatment as treatment for PV.
- Provision of study treatment is not permitted under the laws and regulations of the patient's country.

7. PATIENT DISCONTINUATION/WITHDRAWAL

Details on study and site closures are provided in [Appendix 7](#).

7.1 DISCONTINUATION OF STUDY TREATMENT

Patient must discontinue study treatment if they experience any of the following:

- Pregnancy
- Unacceptable toxicity as determined by Investigator.
 - For cardiac changes:

If a clinically significant finding is identified (including, but not limited to QTcF ≥ 500 ms and/or an increase of ≥ 60 ms in QTcF from screening), the Investigator or qualified designee will determine if the patient can continue in the study and if any change in clinical management is needed. This review of the ECG printed at the time of collection must be documented. Any new clinically relevant finding should be reported as an AE.
- Any medical condition that the Investigator or Sponsor determines may jeopardize the patient's safety if he or she continues in the study.
- Investigator or Sponsor determines it is in the best interest of the patient.
- Disease progression at any point ([Appendix 1](#)).

Study treatment may be discontinued due to non-compliance (e.g., consistent failure to show up for scheduled visits) or if no evidence of clinical benefit in the form of lack of achieving a CR or PR per the ELN 2009 criteria, lack of achieving a Hct response or lack of decreased phlebotomy requirement at Week 32 assessment (see [Appendix 1](#)).

Patients who discontinue study treatment prematurely will be asked to return to the clinic for a study completion/early termination visit (see Section [8.9.3](#)) and may undergo follow-up assessments (see Section [8.9.4](#)). The primary reason for premature study treatment discontinuation should be documented on the appropriate eCRF. Patients

who discontinue study treatment prematurely for reasons other than progression or NR (withdraw prior to Week 32) may be replaced.

7.1.1 Temporary Interruption and Discontinuation

Table 6 shows the general guidance for dosing delay due to AEs. For details of temporary interruption secondary to specific AEs, see Section 8.3.9.

Table 6 General Guidance for Dosing Delay

Clinical Event Grade	
1	No dose modification required. ^a
2	No dose modification necessary. ^a
3	Duration ≤ 2 weeks: Hold further dosing until resolution to Grade ≤ 1 and then, resume at original dose or 100 mg. ^{b, c, d} Duration > 2 weeks, but ≤ 4 weeks: dose reduce to 100 mg. ^d Duration > 4 weeks: discontinue treatment. ^e
4	Duration ≤ 4 weeks: Hold further dosing until resolution to Grade ≤ 1, resume at 100 mg. ^d Duration > 4 weeks: discontinue treatment. If the Grade 4 AE recurs (a second time), then idasanutlin should be discontinued.

AE = adverse event.

- ^a Grade 1 or 2 AEs do not necessarily require dose holding or modification unless specifically noted in Table 8 (Guidelines for Managing Hematologic Toxicity). For Grade 2 events, idasanutlin can be resumed at the same dose when the event resolves to at least Grade 1.
- ^b Dose-reduction is allowed to 100 mg idasanutlin if by collective Investigator and Sponsor judgment that such a change is warranted.
- ^c Patients with Grade 3 AEs that are clearly unrelated to the study drug in the opinion of the Investigator and Sponsor and for which restarting/continuing idasanutlin does not pose a safety risk are allowed to continue receiving therapy without a necessary dose hold or modification.
- ^d If the patient is on 200-mg dose level, idasanutlin will resume at 150 mg (i.e., 50 mg dose reduction).
- ^e The decision to extend the dose delay will be made on the basis of the Investigator's assessment of ongoing clinical benefit and in consultation with the Medical Monitor.

7.2 WITHDRAWAL FROM THE STUDY

Patients have the right to voluntarily withdraw from the study at any time for any reason.

In addition, the Investigator has the right to withdraw a patient from the study at any time. Reasons for withdrawal from the study may include, but are not limited to, the following:

- Any medical condition that the Investigator or Sponsor determines may jeopardize the patient's safety if he/she continues in the study.

- Investigator or Sponsor determines it is in the best interest of the patient.
- Patient non-compliance.

If possible, information on reason for withdrawal from the study should be obtained. The primary reason for withdrawal from the study should be documented on the appropriate eCRF. Patients will not be followed for any reason after consent has been withdrawn.

When a patient voluntarily withdraws from the study, or is withdrawn by the Investigator, samples collected until the date of withdrawal will be analyzed, unless the patient specifically requests for these to be discarded or local laws require their immediate destruction. A patient's withdrawal from this study does not, by itself, constitute withdrawal of specimens donated to the Research Biosample Repository (RBR).

Patients who withdraw from the study after Week 32 assessments will not be replaced. Patients who withdraw prior to Week 32 from the study for reasons other than NR or PD may be replaced.

7.3 LOST TO FOLLOW-UP

A patient will be considered lost to follow-up if he/she repeatedly fails to return for scheduled visits and is unable to be contacted by the study site.

The following actions must be taken if a patient fails to return to the clinic for a required study visit:

- The site must attempt to contact the patient and reschedule the missed visit as soon as possible, counsel the patient on the importance of maintaining the assigned visit schedule and ascertain whether or not the patient wishes to and/or should continue in the study.
- In cases in which the patient is deemed lost to follow-up, the Investigator or designee must make every effort to regain contact with the patient (where possible, 3 telephone calls and, if necessary, a certified letter to the patient's last known mailing address or local equivalent methods). These contact attempts should be documented in the patient's medical record.
- Should the patient continue to be unreachable, he/she will be considered to have withdrawn from the study with a primary reason of lost to follow-up.

8. STUDY ASSESSMENTS AND PROCEDURES

Study procedures and their timepoints are summarized in the SoA (Section 1.2).

Protocol waivers or exemptions are not allowed.

Immediate safety concerns should be discussed with the Sponsor immediately upon occurrence or awareness to determine if the patient should continue or discontinue study treatment.

Procedures conducted as part of the patient's routine clinical management (e.g., blood count) and obtained before signing of the ICF may be utilized for screening or baseline purposes provided the procedure met the protocol-specified criteria and were performed within the time-frame defined in the SoA.

